4.1.1 Imputation Methods for Missing Data

Intercurrent events, inducing missing assessments, may occur during the course of the study for various reasons such as:

- treatment discontinuation due to an adverse event or a lack of efficacy,
- treatment discontinuation due to subject noncompliance (protocol deviations, missing two consecutive visits).

The potential impact of missing data due to missing a visit, treatment/study discontinuation or loss-to-follow-up on the trial conclusions may be evaluated with several approaches based on different plausible assumptions that account for the uncertainty due to this unobservable data.

These approaches will be Non-Responder Imputation (NRI), Last Observation Carried Forward (LOCF), Multiple Imputation (MI) and Tipping Point Analysis (TPA).

The extent of missing data will be documented with descriptive analyses (refer to Section 4.6.3) and may be assessed with complete case analyses.

The sensitivity analyses for the efficacy endpoints (using the approaches below) that are not pre-planned in Table 4.4 will only be performed if the extent of missing data is greater than 10%. Missing data include any data that are imputed i.e. any missing assessments or subjects who discontinue study treatment but remain in the study.

The methods to handle missing efficacy variables are summarized in Table 4.4.

Table 4.4: Analysis Populations and Imputation Approaches to Handle Missing Data in Function of Efficacy Variables

Type of Variables	Variables	Period (Week – Week)	Analysis Population	Imputation (See Section 4.1.1)	IA1	IA2*	Final					
Binary	Primary: IGA score of 0 or 1 at Week 12	0-12	ITT	NRI	●		●					
				None (CC)			(●)					
				LOCF	●		●					
				TPA			(●)					
				MI			(●)					
				MITT12	NRI	●		●				
	Secondary: PASI responses	0-12	ITT	NRI	NRI	●		●				
					None (CC)			(●)				
					MI			(●)				
					MITT12	NRI	●		●			
					PP12	NRI	●		●			
					Secondary: PASI responses and IGA score of 0 or 1 after Week 12	12-24	ITT	NRI	NRI		●	●
	None (CC)			(●)								
	LOCF (IGA only)		●	●								
	MITT24	NRI		●					●			
	PP24	NRI		●					●			
	24-52	ITT	NRI	NRI					NRI			●
									None (CC)		● ⁺	(●)
									LOCF (IGA only)			●
									MITT48	NRI		
Exploratory: Achievement DLQI of 0 or 1	0-24	ITT	NRI	NRI						●	●	
				24-48	ITT	NRI			●			

Type of Variables	Variables	Period (Week – Week)	Analysis Population	Imputation (See Section 4.1.1)	IA1	IA2*	Final
Binary	Exploratory (escalation): IGA score of 0 or 1, IGA score of 0, PASI responses	12-24	MITT24 & subjects who escalated due to IGA > 1	NRI		●	●
			Week 12 IGA non-responder	NRI			(●)
	12-52	MITT48 & subjects who escalated due to IGA > 1	NRI			●	
	Exploratory (dose hold): IGA score of 0 or 1, IGA score of 0, PASI responses during the M1095 dose hold interval, PASI responses after M1095 restart	24-52	MITT48 & subjects who are eligible to dose hold	None (CC)		●	●
Categorical	Secondary: Shift from baseline in IGA score category	0-12	ITT	LOCF	●		●
		12-24	ITT	LOCF		●	●
		24-52	ITT	LOCF			●
	Exploratory (escalation): Shift from Week 12 in IGA score category	12-24	MITT24 & subjects who escalated due to IGA > 1	LOCF		●	●
			Week 12 IGA non-responder	LOCF			(●)
	12-52	MITT48 & subjects who escalated due to IGA > 1	LOCF			●	
Exploratory (dose hold): Shift from Week 24 in IGA score category	24-52	MITT48 & subjects who are eligible to dose hold	None (CC)			●	
Time-to-event	Secondary: Time to first IGA/complete IGA response from baseline	0-52	ITT	None		● ⁺	●
	Exploratory (escalation): Time to first IGA/complete IGA response from Week 12	12-52	MITT24 & subjects who escalated due to IGA > 1	None		● ⁺	●
	Exploratory (dose hold): Time to first IGA ≥ 1 from Week 24, time to first complete IGA response from M1095 restart	24-52	MITT48 & subjects who are eligible to dose hold	None		● ⁺	●

Type of Variables	Variables	Period (Week – Week)	Analysis Population	Imputation (See Section 4.1.1)	IA1	IA2*	Final
Continuous	Secondary: change and percent change from baseline in PASI	0-12	ITT	LOCF	●		●
				None (CC)			(●)
				MI			(●)
		12-24	ITT	LOCF		●	●
				None (CC)			(●)
		24-52	ITT	LOCF			●
	None (CC)				● ⁺	(●)	
	Secondary: Absolute change from baseline in percentage of total BSA affected by plaque-type psoriasis	0-12	ITT	LOCF		●	●
				None (CC)			(●)
		12-24	ITT	LOCF		●	●
				None (CC)			(●)
		24-52	ITT	LOCF			●
				None (CC)		● ⁺	(●)
	Exploratory: change from baseline in DLQI, SF-36, EQ-PSO	0-12	ITT	LOCF		●	●
		12-24	ITT	LOCF		●	●
		24-48	ITT	LOCF			●
	Exploratory (escalation): change and percent change from baseline/Week 12 in PASI	12-24	MITT24 & subjects who escalated due to IGA > 1	LOCF		●	●
				Week 12 IGA non-responder			(●)
		24-52	MITT24 & subjects who escalated due to IGA > 1	LOCF		● ⁺	●
				Week 12 IGA non-responder			(●)
12-52		MITT48 & subjects who escalated due to IGA > 1	LOCF			●	
			None (CC)		● ⁺	●	
Exploratory (dose hold): raw PASI scores, raw PASI scores during the M1095 dose hold interval, after M1095 restart by visits and as a function of time in weeks, change and percent change in PASI from baseline/Week 24	24-52	MITT48 & subjects who are eligible to dose hold	None (CC)		● ⁺	●	

Note: (●) indicates the sensitivity analyses that are optional and may be performed.

*: The list for IA2 may not be exhaustive and additional analyses planned for final analysis may be included in IA2 if deemed necessary – this will be confirmed before unblinding.

†: Only data up to a cutoff date, which is beyond Week 24 (Visit 13) for the last subject are presented.

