*** Prior to Week 24**

M1095 subjects in Arms 2 and 3 will receive placebo at Week 1, 3, 6, 10 and 14.
 M1095 subjects in Arm 4 will receive placebo at Week 1, 3, 6, 10, 14 and 16.
 M1095 subjects in Arm 5 will receive placebo at Week 1, 3 and 14.
 Secukinumab subjects in Arm 6 will receive placebo at Week 6, 10 and 14.

Exposure to Placebo will be limited to a maximum of 12 weeks during the induction period and a maximum of 20 weeks after Week 24 (i.e. during the response assessment/dose hold period) provided that the subjects maintain a complete remission (i.e. achieving an IGA = 0).

All subjects, irrespective of whether they completed or discontinued the study, will be followed up for safety and potential sustainability of efficacy, for an additional 8 weeks (56 days) after receiving the last dose of study treatment. In addition, subjects who discontinued prior to Week 52 will be contacted monthly as per the study schedule (up to Week 52) to report any AEs, concomitant medications and any new psoriasis treatments.

2 Interim Analyses

Two Interim Analyses (IAs) are planned during this trial:

1. IA1: the first unblinded IA of complete 12-week data for all randomized subjects will occur at the end of the induction period, while the study is still ongoing,
2. IA2: the second IA will occur at the completion of the maintenance/escalation period at Week 24, while the study is still ongoing.

The purpose of both interim analyses is to closely monitor the safety and tolerability data throughout the study. The study will not be terminated early on the basis of either positive efficacy or futility after the review of the first or the second interim analyses. The two interim analyses are also conducted to gather preliminary efficacy information to make possible executive decisions concerning the clinical project.

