(6) - Secukinumab 300 mg at Week 0, 1, 2, 3, 4, 8 (and 12 and Q4W)	Secukinumab
(2) - M1095 30 mg at Week 0, 2, 4, 8 (2a) and Q4W if no escalation at Week 12 (2b) and M1095 120 mg Q4W if escalation at Week 12	30mg (x4), Q4
(3) - M1095 60 mg at Week 0, 2, 4, 8 (3a) and Q4W if no escalation at Week 12 (3b) and M1095 120 mg Q4W if escalation at Week 12	60mg (x4), Q4
(4) - M1095 120 mg at Week 0, 2, 4, 8 (and 12 and Q8W)	120mg (x4), Q8
(5) - M1095 120 mg Q2W at Week 0, 2, 4, 6, 8, 10 (and 12 and Q4W)	120mg (x6), Q4
	Total M1095 ^c

a: Subjects will be assigned to a treatment group based on the actual treatment they received most during the overall period for all treatment groups except for (1), (2b) and (3b). Regarding (2b) and (3b), subjects will be assigned to a treatment group based on the actual treatment they received most during the induction period.

b: Plac/120 mg (x4), Q4 include all subjects who were mostly administered M1095 120 mg from Week 12 to Week 44 having received placebo during the induction period. The data will only be presented from Week 12 onwards for this treatment group.

c: Total M1095 will include all subjects who received M1095 at any time during the study i.e. (1), (2), (3), (4) and (5).

All pairwise treatment comparisons will be two-sided at the 5% level, without adjustment for multiplicity unless otherwise specified.

All primary/secondary efficacy and exploratory QoL endpoints will be presented in tables including visits from Week 0 to Week 52 as follows: 0, **1, 2, 3, 4, 6, 8, 10, 12**, // 14, 16, 20, **24**, // 28, 32, **36**, 40, 44, **48** and 52 (each week number, written in bold, indicates the weeks, at which the pairwise treatment comparisons will be made and // indicates the boundary for the study periods). In regard to interim analyses, only visits up to Week 12 will be included for IA1. IA2 will include data up to Week 24 for all subjects and beyond Week 24 for some subjects depending on the cut-off date (see Section 2). The analyses may be split by period or by combined periods depending on the tables produced for IA1 and IA2.

For all efficacy and quality of life analyses unless specified otherwise, baseline will be defined as the last non-missing assessment prior to the first dose of study medication (planned at Week 0).

For safety analyses, baseline will be defined differently according to the treatment period:

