4.1.1.1 Complete Cases (CC)

Where stated, efficacy and quality of life data will be analyzed without any imputation using complete cases to assess the imputation approaches. A complete case will be a subject with no missing data at the considered timepoint and who did not discontinue treatment during this period before this timepoint.

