4.1.1.2 Non-Responder Imputation (NRI)

Where specified, missing dichotomous categorical efficacy data (such as clinical response) will be imputed with Non-Responder Imputation (NRI). NRI will assume a non-response for the considered endpoint at any assessment that is missing. This may arise because of a missed assessment, discontinuation due to any reasons from study treatment or study at any time point prior to the cutoff analysis date regardless of whether the subject was a responder at the time of dropout.

NRI will be the primary imputation approach for the primary and key secondary analyses (as specified in Table 4.4).

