4.2.2 Secondary Analyses

All subjects in the ITT population will be included in the secondary efficacy analyses.

The main estimands of the secondary objectives of longer-term efficacy after Week 12:

- for the binary endpoint IGA (and the key secondary endpoints PASI 75 / PASI 90 / PASI 100) is the difference in response proportions between treatment conditions at:
 - Week 24,
 - Week 36,
 - Week 48
- for the continuous endpoint PASI score (and the other secondary endpoint percentage of total BSA affected by plaque-type psoriasis) is the difference in means between treatment conditions in the change from baseline to:
 - Week 24,
 - Week 36,
 - Week 48

in the ITT population regardless of whether or not escalating to the M1095 120 mg from Week 12 or having dose held at Week 24 had occurred.

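### At the second interim, whole-arm response rates switch from non-responder imputation to complete cases after Week 24, which biases the later rates upward by about p x d

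*SAP*

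**What the plan says.** SAP Table 4.4 sets the imputation method by endpoint, period and analysis. For the ITT population in the row "Secondary: PASI responses and IGA score of 0 or 1 after Week 12":

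- **Weeks 12-24:** NRI is marked for IA2 and Final.
- **Weeks 24-52:** NRI is marked for Final only. Complete cases are marked for IA2 and are optional at Final. LOCF (IGA only) is marked for Final only.

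The rows for change in PASI and in BSA follow the same pattern: LOCF at IA2 to Week 24, then complete cases at IA2 and LOCF at Final. The IA2 marks after Week 24 carry a footnote: "Only data up to a cutoff date, which is beyond Week 24 (Visit 13) for the last subject are presented". SAP Section 4.1 explains that "IA2 will include data up to Week 24 for all subjects and beyond Week 24 for some subjects depending on the cut-off date".

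Section 4.1.1.1 defines a complete case as "a subject with no missing data at the considered timepoint and who did not discontinue treatment during this period before this timepoint". Under Section 4.1.1.2, NRI counts a missing assessment as a failure, including one caused by "discontinuation due to any reasons from study treatment or study at any time point prior to the cutoff analysis date". The longer-term estimand in Section 4.2.2 is a difference in ITT proportions at Weeks 24, 36 and 48, "regardless of whether or not escalating to the M1095 120 mg from Week 12 or having dose held at Week 24 had occurred". On the use of IA2, Section 2 says: "The two interim analyses are also conducted to gather preliminary efficacy information to make possible executive decisions concerning the clinical project".

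**The concern.** A subject lost before Week 24 is a failure in the denominator up to Week 24 and then drops out of the denominator. The reported rate can therefore rise at the point where the method changes, with no change in any subject. That point is also when M1095 is first withheld from some subjects, so readers will look closely at the series there.

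The choice also sits badly with the rest of the SAP. Section 4.1.1.2 makes NRI the main approach for the key secondary analyses, as specified in Table 4.4. Table 4.5 counts PASI 75/90/100 up to Week 48 among the key secondary variables. Section 4.1.1.1 gives complete cases the role of checking the imputation methods, yet after Week 24 no imputed ITT response analysis is marked at IA2 for them to check.

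The excluded subjects are unlikely to be a random subset. Section 4.1.1 names adverse events and lack of efficacy as reasons for discontinuation. Protocol Section 6.6.2 asks investigators at Week 24 to consider discontinuing subjects whose psoriasis is worse than at baseline.

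At stake is how interim information that may feed project decisions is read. The primary and final analyses are not affected.

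**Working it through.** **Plan's own figures.** The documents state no figure for this switch. The 50 per arm used below comes from Protocol Section 9.2. The power given there for PASI 100 (45% against 72%, two-sided 0.05, about 79%) reproduces as 79.1%, but the point does not depend on it.

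**Who leaves the denominator.** Someone who stops treatment within the 24-52 period fails the second limb of the complete-case definition. Someone who stopped before Week 24 fails the first limb: after the Early Discontinuation visits, Protocol Section 8.1.11 provides telephone contact only, so no efficacy assessment exists. A dose-held subject is different. Such a subject receives placebo, which Protocol Section 6.0 counts as study drug, and so remains a complete case.

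**Formula.** Among subjects whose visit is due, let p be the response rate in those observed and still on treatment, and d the share missing or discontinued. The number of responders is the same under both methods; only the denominator differs.

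- NRI rate = p(1 - d)
- Complete-case rate = p
- Excess = p - p(1 - d) = p x d

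**Size, in percentage points.** All values of d are assumed. The 45% and 72% are the Week 12 PASI 100 planning rates; 60% and 85% are assumed.

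| p | d = 0 | d = 5% | d = 10% | d = 15% |
|---|---|---|---|---|
| 45% | 0 | 2.3 | 4.5 | 6.8 |
| 60% | 0 | 3.0 | 6.0 | 9.0 |
| 72% | 0 | 3.6 | 7.2 | 10.8 |
| 85% | 0 | 4.3 | 8.5 | 12.8 |

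**Illustration.** Take 50 in an arm, with 5 lost by Week 24 and 40 of the other 45 responding, all with Week 28 due.

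- Week 24: NRI 40/50 = 80.0%; complete cases 40/45 = 88.9%.
- Four responders then lose response and stay. Week 28 complete cases: 36/45 = 80.0%. The series as planned reads 80.0% to 80.0%; NRI throughout reads 80.0% to 72.0% (36/50).
- The same four instead stop treatment. Week 28 complete cases: 36/41 = 87.8%, an apparent rise; NRI is again 72.0%.

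**Why plain NRI is not the remedy.** If 10-20% of subjects have not reached the visit at the cut-off, counting them as failures turns a true 80% into 72% (80 x 0.9) down to 64% (80 x 0.8).

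**The case against.** **The cut-off makes complete cases natural.** After Week 24 only some subjects have data at IA2, and plain NRI would fail visits not yet due. That rules out plain NRI but does not require dropping discontinuers. The NRI definition already refers to the analysis cut-off date, and Table 4.4 already marks LOCF with the cut-off footnote at IA2 for PASI change in escalated subjects over Weeks 24-52.

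**The series may never be joined.** Week 24 falls in both period rows, and Section 4.1 allows outputs to be split by period, so a complete-case Week 24 value might be shown beside Week 28. This stands as a possibility. But Section 4.2.2.2.1 plans line plots to Week 48, and splitting the tables would not remove the gap between IA2 and Final.

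**The SAP leaves room for more.** A note to Table 4.4 allows final-type analyses to be added at IA2. It permits NRI after Week 24 without committing to it. The marks for NRI in the MITT48 population are not legible in the available text, so the point is confined to the ITT rows.

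**The stakes are limited.** This stands. IA2 has no stopping rule for efficacy or futility, and Final uses NRI in ITT in both periods.

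**A reader might infer that the switch conceals loss of response after withholding.** The documents do not support that. Held subjects who lose response and stay are counted as failures. The dose-hold analyses marked for IA2, including time to first IGA of 1 or more, are separate and have no change of method. Their response rows are complete-case throughout, however, so they too lose subjects who leave.

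**Conclusion.** The point holds for the whole-arm ITT series at IA2. After Week 24 the planned response rates exceed the NRI rate by p x d: about 4 to 13 points at p = 85%, or 3 to 9 points at p = 60%, for d of 5-15%. These are scenarios, since neither p nor d after Week 24 is given. The excess depends on each arm's own dropout, so comparisons between arms can shift as well. A real whole-arm decline of similar size could be offset.

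Two firmer statements would go too far. One is that rates will jump after Week 24: with no dropout the step is zero, and a real loss can cancel it. The other is that IA2 rates will fall at Final for purely methodological reasons, which again requires dropout. For PASI and BSA change the switch is plain, but p x d does not apply and neither size nor direction can be derived. This is a worthwhile, inexpensive correction to an interim analysis.

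**What to change.** Amend Table 4.4 for IA2 visits after Week 24:

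1. **Denominator:** all ITT subjects whose visit, taken as the end of its window counted from Week 0, fell on or before the cut-off date, including those who discontinued earlier. Week 28, for example, is Day 197 with a window of 5 days either side in the Schedule of Activities, so it is due once Day 202 has passed. The same calendar rule for everyone treats discontinuers and continuers alike.
2. **Method:** NRI in that set, leaving out only visits not yet due. In the illustration this gives 80.0% to 72.0%, with no step from the method itself.
3. **Display:** number due, observed and discontinued, by arm and visit.
4. **Complete cases:** keep as supportive.
5. **PASI and BSA change:** LOCF in the same set, solely for consistency with the Weeks 12-24 and Final rows. LOCF carries forward a discontinuer's last value and so does not itself protect against masking; the SAP should say so.

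The cost is SAP wording and a due-date flag in the IA2 dataset. IA2 response rates will be less favourable by p x d.

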4.1.1.1 Complete Cases (CC)

Where stated, efficacy and quality of life data will be analyzed without any imputation using complete cases to assess the imputation approaches. A complete case will be a subject with no missing data at the considered timepoint and who did not discontinue treatment during this period before this timepoint.

4.1.1.2 Non-Responder Imputation (NRI)

Where specified, missing dichotomous categorical efficacy data (such as clinical response) will be imputed with Non-Responder Imputation (NRI). NRI will assume a non-response for the considered endpoint at any assessment that is missing. This may arise because of a missed assessment, discontinuation due to any reasons from study treatment or study at any time point prior to the cutoff analysis date regardless of whether the subject was a responder at the time of dropout.

NRI will be the primary imputation approach for the primary and key secondary analyses (as specified in Table 4.4).

4.1.1.3 Last-Observation Carried Forward (LOCF)

Where stated, missing categorical and continuous efficacy data will be imputed with Last Observation Carried Forward (LOCF). LOCF approach will consist in carrying forward the value of the last observed non-missing post-baseline assessment to the subsequent scheduled and missing assessment. In case of missing baseline i.e. of absence of an observed assessment prior to the first administration of treatment at Week 0, no imputation of baseline will be performed. In addition, if a subject did not have at least one observed post-baseline assessment during the considered period, no LOCF will be performed on the missing post-baseline assessments.

This approach will assume that any subjects who withdraw the treatment or study due to any reasons maintain the same value that was observed at the last non-missing post-baseline assessment before withdrawing. Similarly, for subjects who miss an assessment, the approach will assume that they maintain the same value that was observed at the last non-missing post-baseline assessment until they return to a visit and a new value is observed.

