4.1.1.4 Multiple Imputation (MI)

Missing pre-specified categorical and continuous efficacy data will be imputed with MI under Missing at Random (MAR) assumption using the ITT population (Enders, 2010). MI method will be applied on the data of a given endpoint that are assumed to be MAR.

The current assumption on which the primary analysis is based is that all subjects with a missing response at a given timepoint and/or with missing responses after treatment withdrawal are regarded as non-responder, non-response is assumed regardless of whether the subject responded to the treatment at the time of the drop-out. The secondary analyses using LOCF approach assume that all subjects with missing data at a given timepoint and/or after treatment withdrawal maintain their last observed assessment over time.

MI under MAR assumption assumes that dropouts behave similarly to other subjects in the same treatment group who did not withdraw and continued to be treated with the study treatment. In terms of efficacy, this will estimate the effect of treatment as if all subjects were treated as randomized.

MI will be implemented in three steps using SAS[®], version 9.4 or higher (see Figure 4.1.). Depending on the nature of data, some of the steps may have some specificities (Demirtas et al., 2008). MI method assumes a multivariate normal distribution for the continuous variable of interest (e.g. PASI percent change) at each visit.

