4.3 Quality of Life

All subjects in the ITT population will be selected for the analyses of Quality of Life (QoL) variables.

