4.3.1 Variables

The QoL variables are:

- Change from baseline in Dermatology Life Quality Index (DLQI) total score and in DLQI subscales,
- Achievement of DLQI of 0 or 1 (binary variable),
- Change from baseline in the norm-based Short Form 36 (SF-36) scores for the eight sections and for the physical and mental summary components,
- Change from baseline in EuroQuality of Life Questionnaire for Psoriasis (EQ-PSO) as measured by VAS and EQ-PSO score for the 7 dimensions.

The derivations of QoL scores are described in the Appendices on page 68.

LOCF will be used to impute any missing values for the continuous variables and NRI for the binary variable (refer to Section 4.1.1.3).

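### An undefined period limit on LOCF (SAP 4.1.1.3), read with the Table 4.4 periods, drops earlier leavers from the ITT LOCF analyses at Weeks 24, 36 and 48

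*SAP*

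**What the plan says.** SAP 4.1.1.3 sets the LOCF rule. Its first paragraph ends with a limit: "if a subject did not have at least one observed post-baseline assessment during the considered period, no LOCF will be performed". Its second paragraph gives the assumption behind the method: "This approach will assume that any subjects who withdraw the treatment or study due to any reasons maintain the same value" as at the last non-missing post-baseline assessment. Section 4.1.1.4 repeats that assumption for the secondary LOCF analyses, where "all subjects with missing data at a given timepoint and/or after treatment withdrawal maintain their last observed assessment over time".

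Section 4.2.2 states that "All subjects in the ITT population will be included in the secondary efficacy analyses". It defines the longer-term estimands at Weeks 24, 36 and 48 in the ITT population, whether or not escalation or dose hold occurred.

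Table 4.4 assigns ITT with LOCF in separate period rows:
- change and percent change in PASI, BSA change and IGA shift: Weeks 0-12, 12-24 and 24-52;
- continuous QoL: Weeks 0-12, 12-24 and 24-48;
- supplementary IGA response by LOCF after Week 12: Weeks 12-24 and 24-52.

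Section 4.1 lists the visits with a mark after Week 12 and after Week 24 that "indicates the boundary for the study periods". It adds that "The analyses may be split by period or by combined periods depending on the tables produced for IA1 and IA2".

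**The concern.** The term *considered period* is not defined where it decides who is imputed. In 4.1.1.4.1, 4.8 and 4.9.2.5 the SAP uses it for a single study period, such as induction. With the Table 4.4 rows, a programmer could reasonably apply the limit row by row. Anyone who left before the period began would then have no value in it and would disappear from that period's LOCF analysis. The assumption stated one paragraph later would have kept that subject in.

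The results concerned are percent change in PASI at Weeks 24, 36 and 48 (tested by ANCOVA, 4.2.2.2.3), continuous QoL at the same weeks (tested but exploratory, 4.3.2), the supplementary IGA LOCF analysis, and the descriptive summaries of BSA change and IGA shift. After Week 12, LOCF is the only ITT analysis of PASI change that Table 4.4 commits to for the final report; complete-case analysis is optional and there is no MI row. Two results at the same visit could both be labelled ITT, with NRI counting the leavers as failures and LOCF omitting them.

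**Working it through.** The plan gives no figure on this point, so there is none to reproduce. The check applies the rule to the visit schedule.

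**Inputs.** Post-baseline PASI, BSA and IGA visits: Weeks 1, 2, 3, 4, 6, 8, 10, 12, 14, 16, 20, 24, 28, 32, 36, 40, 44, 48, 52. Post-baseline QoL visits: Weeks 12, 24, 36, 48 (Protocol 1.3). After the Early Discontinuation visits, contact is by telephone and collects no efficacy or QoL data (Protocol 8.1.11).

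**Two boundary readings.** (A) Weeks 12 and 24 only close a period, as the marks in SAP 4.1 suggest: 1-12, 14-24, 28-52. (B) They also open the next, as the Table 4.4 labels, 4.2.2.2.1 and the Week 12-24 visit list in 4.2.3.1.2 allow.

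**Count.** For each target week, list every earlier visit at which a subject could last be seen with a post-baseline value in hand. Then count those that leave no value in the target's period.

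| Target | PASI/BSA/IGA: possible last visits | Barred (A) | Barred (B) | QoL: possible last visits | Barred (A) | Barred (B) |
|---|---|---|---|---|---|---|
| Week 24 | 11 | 8 | 7 | 4 | 4 | 0 |
| Week 36 | 14 | 12 | 11 | 7 | 7 | 4 |
| Week 48 | 17 | 12 | 11 | 10 | 7 | 4 |

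For Week 24 PASI, the 8 under A are Weeks 1, 2, 3, 4, 6, 8, 10 and 12; reading B frees Week 12. QoL counts start at Week 12, since no rule could impute before a first post-baseline value. Without the limit, every barred count is 0. These are counts of schedule positions, not shares of subjects.

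**Early Discontinuation visits.** These can supply an in-period value. At last dose plus 4 weeks, induction doses at Weeks 0, 1, 2, 3, 4, 6, 8, 10 give visits at Weeks 4, 5, 6, 7, 8, 10, 12, 14. Of these, 1 of 8 falls in the second period under A (Week 14) and 2 of 8 under B (Weeks 12 and 14). If the 56-day visit also collects efficacy, doses at Weeks 6, 8 and 10 give Weeks 14, 16 and 18, making 3 of 8 under A. A Week 20 dose would likewise give Week 28. The Protocol is mixed here: 7.0 describes 28- and 56-day returns with the Early Discontinuation content, while 7.2 and 8.1.11 limit day 56 to safety follow-up.

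**Precision (illustration).** If 5%, 10% or 20% of an arm of 50 is dropped, 47.5, 45 or 40 remain. The standard error rises by 1/√(1−d), that is 2.6%, 5.4% or 11.8%.

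**Shift against the SAP's own assumption (illustration).** Let d be the share leaving before Week 12, f the share of leavers with an in-period value, and g the leaver-stayer gap in last PASI percent change. The arm mean moves by g × [d − df/(1 − d + df)]. With d = 0.10 and g assumed between 0 and 60 points:
- f = 0: 60 × 0.10, so 0 to 6.0;
- f = 1/8: 60 × (0.10 − 0.0125/0.9125), so 0 to 5.2;
- f = 3/8: 60 × (0.10 − 0.0375/0.9375), so 0 to 3.6.

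With equal d, f and g in two arms, the difference between them moves by 0. With 10% against 5% leaving and f = 0, it moves by 60 × 0.05, so 0 to 3.0. If leavers' last values were better than stayers', the sign would reverse. None of d, f or g has a source in the documents, and using visit fractions for f assumes last doses are spread evenly.

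**The case against.** The strongest reply is that the limit is a stated exception to a general assumption, and a defensible one. Treatment changes at Weeks 12 and 24, and carrying Arm 1 placebo values into results labelled as M1095 120 mg is unattractive. That has force as a design preference. But it does not explain barring arms whose treatment did not change, and neither assumption paragraph mentions an exception.

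A second reply is that the period may run from baseline to the visit analysed, or that periods may be combined. The SAP permits combined tables, so intent is not settled. Under that permission, however, the analysed set could depend on how the tables are split.

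Several stronger inferences are tempting and should not be drawn:
- *QoL is hit hardest.* Only under reading A can QoL at Weeks 24 and 36 not be filled from an earlier scheduled visit. Under B, Week 24 can be filled from Week 12 and Week 36 from Week 24.
- *Early Discontinuation visits hardly ever help.* That depends on the boundary and on what the 56-day visit collects.
- *The QoL sections contradict the rule.* Section 4.3.1 says "LOCF will be used to impute any missing values for the continuous variables" but refers to 4.1.1.3, and 4.3 only names the population. A population statement does not promise everyone a value, so the conflict rests on 4.1.1.3, 4.1.1.4 and the estimand in 4.2.2.

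**Conclusion.** The point holds as an undefined term with a real consequence. On the reading closest to the SAP's own usage, ITT subjects who left in an earlier period drop out of the LOCF analyses at Weeks 24, 36 and 48, against the stated carry-forward assumption and the ITT estimand. This survives either boundary reading: for PASI, 7 or 8 of 11, 11 or 12 of 14, and 11 or 12 of 17 possible last visits are barred. It disappears only if the period means baseline to the visit analysed or the periods are combined.

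A reader might infer that the later PASI results are inflated by a known number of points. The documents do not support that: they give no dropout rate and no leaver-stayer gap. The shift is zero if leavers resemble stayers, and differences between arms move mainly when dropout or the gap differs by arm. The comparison is with the SAP's own assumption, not with an unbiased truth. The Week 12 primary analysis and all NRI analyses (IGA response, PASI 75/90/100, DLQI 0 or 1) are unaffected. This should be corrected, but it does not threaten the main conclusion.

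**What to change.** For the ITT secondary efficacy and QoL analyses, remove the limit to the considered period from the LOCF sentence in SAP 4.1.1.3. Every ITT subject with a baseline and at least one post-baseline value then contributes, however the tables are split. State how Early Discontinuation visits map to scheduled visits. Report the number imputed per arm and visit, and flag values carried across a treatment change, notably Arm 1 placebo values carried past Week 12. Leave the escalation and dose-hold analyses on their own rules.

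If within-period carrying is intended, define the period and its boundary visits, name the reduced analysis set, and reconcile the second paragraph of 4.1.1.3, 4.1.1.4 and 4.2.2 with it.

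The cost is SAP text and programming; no new data are needed. The small downside is that some carried values will precede a treatment change, which the flag makes visible.
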